**Figure 1: Treatment Algorithm**

## 1.1. Schedule of Activities

**Table 1: Schedule of Activities/Assessments**

Study Day:	Screen	BL/ D1	D 2	D 3	D 4	D 5	D 6	D 7	D 8	D 14±3d	D 28±3d	Early Therapy DC	Notes
Examination / Procedure													
Informed consent	X												Study day is relative to Day 1= first dose of study intervention
Eligibility criteria	X	X											
Demographics	X												
Medical history	X	X											
Physical examination / vital signs	X												Record abnormal results as medical history
Height / Weight	X												
Temperature / antipyretic use	X	X	-----→								X		Collect per standard of care through hospital discharge
Electrocardiogram a	X			X									Monitor per standard of care
Pregnancy test (as applicable)	X												Women of childbearing potential
Laboratory assessments – Hematology, Clinical chemistry b – D-dimer, fibrinogen	X	X	X		X		X		X	X	X		Local laboratory – record results in the case report form
– Biomarkers (e.g., HMGB1, IL-6, SAA, TNF $\alpha$ )		X	X	X	X	X	X	X	X	X	X		Store plasma samples for central laboratory analysis
– PT/INR, aPTT c,d	X	X	X	X	X	X	X	X				X	Local Lab. Do not draw from the same line used for drug administration c,d
– Anti-Xa (if applicable)		X	X	X	X	X	X	X				X	To monitor enoxaparin anticoagulation
Pharmacokinetic samples (sites with appropriate capabilities)		X c	X c		X c				X c				D1 predose and end of bolus dose, D2 and D4 anytime, D8/end of continuous infusion. Do not draw from the same line used for drug administration. Central laboratory analysis.
NIAID ordinal scale components – Ventilator use – Oxygen use	X	X	-----→								X		Record date/time for each change in individual components of the assessment e
Sample for virology		X						X					Cohort 3 and Phase 3 only
Randomization		X											

Study Day:	Screen	BL/ D1	D 2	D 3	D 4	D 5	D 6	D 7	D 8	D 14±3d	D 28±3d	Early Therapy DC	Notes
Examination / Procedure													Study day is relative to Day 1= first dose of study intervention
Study intervention – bolus dose		X											
Study intervention – continuous infusion – start/change IV bag		X	X	X	X	X	X	X	End				Begin after bolus dose
Adverse event assessments f	Procedure-related SAEs	X	-----→								X		Record through Day 28
Concomitant medications	X	X	-----→								X		

Abbreviations: aPTT=activated partial thromboplastin time; D=day; INR=international normalized ratio; NIAID (ordinal scale)= National Institute of Allergy and Infectious Diseases (scale used in Study NCT04280705); PT=prothrombin time; HMGB1=high mobility group box protein 1; IL-6=interleukin-6; SAA=serum amyloid A; TNF $\alpha$ =tumor necrosis factor alpha

a Recommend following guidelines of American College of Cardiology. Day 3 ECG not required if participant is on continuous telemetry. Perform unscheduled ECG if irregular heart rhythm on exam or telemetry.

b Refer to Section 8.3.4 and Table 4 for complete list of laboratory tests. Chemistry includes alanine aminotransferase, aspartate aminotransferase, alkaline phosphatase, bilirubin (total and direct), blood urea nitrogen, C-reactive protein, creatinine (with calculated creatinine clearance or estimated glomerular filtration rate), calcium, ferritin, lactate dehydrogenase, magnesium, potassium, and sodium. Hematology includes platelet count, hemoglobin, absolute neutrophil count, and white blood cell count with differential. In the event of thrombocytopenia, refer to the evaluation algorithm in Appendix 6 for additional laboratory tests to diagnose/rule out heparin-induced thrombocytopenia.

c Do not draw blood for aPTT or PK analyses from the same line that is used for study intervention administration. Drawing blood from a heparinized line may falsely alter results obtained; therefore, if using an indwelling catheter, draw approximately 5 mL of blood from the line for discard before drawing the aPTT and PK samples.

d Draw blood for aPTT measurements no sooner than 8 hours after the bolus dose. During the continuous infusion, aPTT should be measured a minimum of once daily; more frequent monitoring is recommended when feasible based on the clinical status of the participant.

e Record date AND time for each change in individual components of the assessment: mechanical ventilation start/stop, high flow/mask oxygen start/stop, nasal oxygen start/stop, hospital discharge (whether with limitations, or without limitations), and death.

f All adverse events must be recorded from the time of administration of the first dose of study intervention until the participant has completed the study (Day 28). However, any study procedure-related SAE that occurs after the study participant has signed the informed consent form and prior to administration of the first dose of study intervention should be recorded as an SAE for the purposes of this protocol.

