In the Phase 2 study of dociparstat for COPD (which was administered to 69 participants as an 8 mg/kg bolus followed by 0.375 mg/kg/hr over 96 hours), there were very few instances of minor/moderate bleeding. During continuous IV infusion of dociparstat, the aPTT was prolonged in all the participants with a mean of  $\leq 8$  seconds from baseline, determined daily. This does not seem to impose added risks for bleeding in this population, in accordance with the findings in healthy volunteers from the 3 Phase I studies with dociparstat; as discussed above, these effects could in fact ameliorate the disseminated intravascular coagulopathy that seems to characterize severe cases of COVID-19. The dociparstat effect on ALT (observed in 37% of dociparstat recipients vs. 11% of placebo recipients in the COPD study) is a class effect to all heparins, heparin derivatives, LMWHs, and heparinoids; this occurs on approximately Day 5 or 7 of exposure with return to baseline values by Day 14 after treatment discontinuation. A total of 50 SAEs were reported during the double-blind portion of the study; of these, 27 SAEs were reported in the placebo group by 14 participants and 23 SAEs reported in the dociparstat group by 17 participants. Eight deaths occurred during the study; 5 in the placebo group and 3 in the

dociparstat group, none of them were considered as related to study intervention by the investigators.

This Phase 2/3 study of dociparstat in participants with severe COVID-19 lung disease seeks to determine whether there is evidence that dociparstat can prevent or mitigate respiratory failure and the need for ventilator support. Dociparstat given as a bolus of 4 mg/kg followed by a continuous infusion for up to 7 days was also generally well tolerated when administered with systemic chemotherapy (anthracycline plus cytarabine for AML, and gemcitabine plus nab-paclitaxel for pancreatic cancer).

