**Table 3: Dosing Regimen: Bolus Dose plus Continuous Infusion**

Study Intervention Dosing	
All Participants:	
 
• Dociparstat 4 mg/kg or placebo IV bolus on Day 1, followed by
 
• Dociparstat or placebo by continuous IV infusion for 24 hours daily for 7 days (starting on Day 1 and ending on Day 8 [168 hours])
 

Dociparstat Continuous Infusion Dose by Cohort	
Phase 2, Cohort 1	
 
• 0.25 mg/kg/hr
 

Phase 2, Cohort 2	
 
• 0.325 mg/kg/hr (dose to be confirmed after DMC review of data from Cohort 1)
 

Phase 2, Cohort 3	
 
• 0.25 or 0.325 mg/kg/hr (dose to be confirmed after DMC review of data from prior cohorts)
 

Phase 3	
 
• 0.25 or 0.325 mg/kg/hr (dose will be the same as used in Cohort 3)
 

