## 7.2. Discontinuation of Study Intervention

In some instances, it may be necessary for a participant to permanently discontinue study intervention before completing the protocol-specified treatment period. Reasons for permanent discontinuation of study intervention may include the following:

- Criteria for restarting study intervention after interruption were not met.
- ALT  $\geq 3$ x ULN (and  $>2$ x baseline value) plus bilirubin  $\geq 2$ x ULN.
- Thrombocytopenia defined as a platelet count of  $<30,000/\text{mm}^3$ .
- Hemorrhagic AE of Grade 3 or higher (graded according to the National Cancer Institute-Common Terminology Criteria for Adverse Events [NCI-CTCAE]).
- Other treatment-related AE of unacceptable severity.
- Condition has improved and participant is eligible for hospital discharge.
- Participant requests to discontinue study intervention.
- Investigator initiates treatment with a therapeutic anticoagulant dose, a thrombolytic agent, or otherwise prohibited therapy that may affect the participant's safety if study intervention were to be continued.
- Investigator determines discontinuation is in the best interests of the participant for safety, behavioral, compliance, or administrative reasons.

Participants who discontinue study intervention early will complete the early discontinuation assessments (refer to the Schedule of Assessments) and will continue to be followed-up through Day 28.

Note: For participants who are discharged from the hospital prior to Day 8, the next visit will be Day 14.

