**Figure 2: HIT Evaluation Algorithm**

**Table 6: The 4Ts Clinical Pretest Probability of HIT**

4Ts	2 points	1 point	0 points
Thrombocytopenia	Platelet count fall $>50\%$ and platelet nadir $\geq 20 \times 10^9/L$	Platelet count fall 30% to 50% or platelet nadir $10-19 \times 10^9/L$	Platelet count fall $<30\%$ or platelet nadir $<10 \times 10^9/L$
Timing of platelet count fall	Clear onset between Days 5 to 14 or platelet fall $\leq 1$ day (if prior heparin exposure within 30 days)	Consistent with Days 5 to 14 fall, but not clear (e.g., missing platelet counts) or onset after Day 14 or fall $\leq 1$ day (if prior heparin exposure 30 to 100 days ago)	Platelet count fall $\leq 4$ days without recent exposure
Thrombosis or other clinical sequelae	New thrombosis (confirmed); skin necrosis at heparin injection sites; anaphylactoid reaction after IV heparin bolus; adrenal hemorrhage	Progressive or recurrent thrombosis; Nonnecrotizing (erythematous) skin lesions; Suspected thrombosis (not confirmed)	None
Other causes of thrombocytopenia	None apparent	Possible (e.g., sepsis)	Probable/Definite (e.g., DIC, medication, within 72 hours of surgery)
Interpretation			
$\leq 3$ points = Low probability ( $<1\%$ )			
4 to 5 points = Intermediate probability ( $\sim 10\%$ )			
6 to 8 points = High probability ( $\sim 50\%$ )			

Source: Pishko AM, Linkins, LA, Warkentin TE, Cuker A. Diagnosis and management of heparin-induced thrombocytopenia (HIT). 2018 Dec. Available at: [https://www.hematology.org/-/media/Hematology/Files/Education/Clinicians/Guidelines-Quality/Documents/ASH\\_VTE\\_HIT\\_PocketGuide.pdf](https://www.hematology.org/-/media/Hematology/Files/Education/Clinicians/Guidelines-Quality/Documents/ASH_VTE_HIT_PocketGuide.pdf)

Adapted from Lo GK, Juhl D, Warkentin TE, et al. Evaluation of pretest clinical score (4Ts) for the diagnosis of heparin-induced thrombocytopenia in two clinical settings. J Thromb Haemost 2006;4:759.

Missing or inaccurate information may lead to a faulty 4Ts score and inappropriate management decisions. Every effort should be made to obtain accurate and complete information necessary to calculate the 4Ts score. If key information is missing, it may be prudent to err on the side of a higher 4Ts score. Reassess frequently. If there is a change in the clinical picture, the 4Ts score should be recalculated.

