Minimum, n (%)																																										
<LLN																																										
Normal																																										
>ULN																																										
Post-Baseline																																										
Maximum, n (%)																																										
<LLN																																										
Normal																																										
>ULN																																										

N = Number of subjects in a specific group; n = Number of subjects with data available; Percentages are based on N;

Normal: Within normal range, LLN: Lower limit of normal, ULN: Upper limit of normal.

Only subjects with baseline and at least one post-baseline value are considered.

Baseline value is defined as the last non-missing measurement prior to, or on the date/time of the first administration of study treatment. NA = not applicable.

Page X of Y

(Notes for programmer:

- generate a post-baseline Maximum Value and post-baseline Minimum Value per subject (incl. unscheduled measurements
- LLN for creatinine clearance is fixed 90 mL/min
- if ULN (eg CC) available, please display n/a
-)

Figure 3: Selected laboratory parameters over time (Box-Whisker-Plot) - Safety Set

Box-Whisker-Plots: by <Parameter> (<unit>), Cohort X, Reference Ranges xxx - yyyy <unit>

y-axis:

range: depending on data
label: Value

x-axis:

range: Visits : Screening, D1 to D28 (depending on data) visit. Incl Early Tx DC at the end of the x-axis.

label: Visit

Box-Whisker Plots:

different styles/colors for the treatment-groups

Plots shifted to not overlap

Default SAS Box-Whisker-Plots - Min, 25%, Median, 75%, Max. Whiskers as 1.5 IQR. Mean included.

Footnotes to be used for the Box-Whisker-Plots :

Visit "Early Tx DC (TXDC)" denotes Early Treatment Discontinuation Visit. Reference Ranges do not necessarily present "values of concern" in this population but will give some context to the results relative to a normal population.

(Notes for programmer:

- replace <Parameter> <unit>, in label by actual parameter and unit used
- Adapt Visits as relevant for the different parameters. Not all parameters are reported for all visits, only scheduled visits to be included in the Figure

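### Table 1 schedules no hematology or chemistry at Early Therapy DC, so participants discharged before the Day 6 draw have no scheduled ALT or platelet result from Day 5 until Day 11–17

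*Protocol*

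**What the plan says.** Protocol Table 1 carries platelets, hemoglobin, ALT, AST and bilirubin in the row "Laboratory assessments – Hematology, Clinical chemistry b – D-dimer, fibrinogen". That row is marked at Screen, D1, D2, D4, D6, D8, D14 and D28. It is blank at D3, D5, D7 and Early Therapy DC. The PT/INR and aPTT row is marked at Screen, D1 to D7 and Early Therapy DC, and is blank at D8. The anti-Xa row matches it except that it has no screening mark.

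Section 7.2 relies on that column: "Participants who discontinue study intervention early will complete the early discontinuation assessments (refer to the Schedule of Assessments"), with follow-up then continuing to Day 28. Its listed reasons for permanent stopping include a platelet threshold, ALT combined with bilirubin, and eligibility for discharge after improvement. It adds: "Note: For participants who are discharged from the hospital prior to Day 8, the next visit will be Day 14".

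The protocol names two periods in which these tests matter. Section 4.3 says of the ALT effect (37% of dociparstat against 11% of placebo recipients in the COPD study) that "this occurs on approximately Day 5 or 7 of exposure with return to baseline values by Day 14 after treatment discontinuation". Appendix 6, Table 6 gives its highest timing score for HIT to "Clear onset between Days 5 to 14".

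On aPTT, footnote d of Table 1 states: "During the continuous infusion, aPTT should be measured a minimum of once daily". Table 3 describes the infusion as "starting on Day 1 and ending on Day 8 [168 hours"].

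**The concern.** A participant who stops treatment attends a visit that measures clotting times but not the platelet count or liver tests by which Section 7.2 itself defines two of the stopping reasons. HIT evaluation in Section 7.1 and Appendix 6 is triggered by the platelet count, and an aPTT cannot stand in for it. If the participant is also discharged, the skip to Day 14 removes the remaining in-hospital draws.

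The analysis would not reveal the loss. SAP Table 14 reports each participant's maximum post-baseline grade and ranks Unknown below Grade 0. A participant whose only post-baseline results are, say, a normal Day 2 and a normal Day 14 value is tabulated as Grade 0, indistinguishable from someone sampled throughout. SAP Section 5.1 places this table in the DMC package, and the DMC's review informs dosing in Cohorts 2 and 3. With 6 and 8 dociparstat participants in Cohorts 1 and 2 (Protocol Section 4.1), one missed case is 1/6 = 17% or 1/8 = 12.5% of an arm.

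**Working it through.** The plan states no figure to reproduce. The check lists the scheduled hematology/chemistry draws for each possible day of stopping with discharge.

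**Inputs**
- In-hospital draws: Days 1, 2, 4, 6 and 8 (Table 1).
- Next visit after discharge before Day 8: Day 14 ± 3, so Day 14 − 3 = 11 to Day 14 + 3 = 17 (Section 7.2, Table 1).
- ALT period: Days 5–7, from Section 4.3.
- HIT timing window: Days 5–14, from Table 6. Assumption: days are counted from Day 1; earlier heparin exposure would shift the window.

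**Formula:** gap = (11 to 17) − day of last scheduled draw. For a Day 5 discharge the last draw is D4, so the gap is 11 − 4 = 7 to 17 − 4 = 13 days.

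| Stop and discharge on | Last scheduled draw | Gap as written (days) | Draw in Days 5–7 | Draw in Days 5–14 | Gap with the row marked at Early Therapy DC (days) |
|---|---|---|---|---|---|
| Day 2 | D2 (D1 if that day's draw is missed) | 9–15 (10–16) | none | only if the visit is on Day 11–14 | 9–15 |
| Day 3 | D2 | 9–15 | none | as above | 8–14 |
| Day 4 | D4 (D2 if that day's draw is missed) | 7–13 (9–15) | none | as above | 7–13 |
| Day 5 | D4 | 7–13 | none | as above | 6–12, gains Day 5 |
| Day 6, before the draw | D4 | 7–13 | none | as above | 5–11, gains Day 6 |
| Day 6, after the draw | D6 | 5–11 | D6 | D6 | 5–11 |
| Day 7 | D6 | 5–11 | D6 | D6 | 4–10, gains Day 7 |

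A participant in hospital through Day 8, whether a completer or an early stopper, has D6 in the ALT period and D6 and D8 in the HIT window. The gap to the Day 14 visit is then 3–9 days.

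**Result**
- The affected group is those who stop and leave before the D6 draw. None has a scheduled draw in Days 5–7, and a Day 14 visit held on Day 15–17 leaves Days 5–14 empty as well.
- The change puts a draw inside both windows for stops on Days 5–7. For discharges on Days 2–4 it secures an end-of-exposure value only. Days 5–7 stay unsampled, and a late Day 14 visit still misses the HIT window.
- The Day 8 aPTT cell bears on neither window, because aPTT measures neither ALT nor platelets.

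**The case against.** Several points on the other side are sound.

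- **Standard-care results are captured.** Protocol Section 8.3.4 requires sites to enter all local laboratory results, and SAP Tables 14 and 16 include unscheduled measurements in the post-baseline extremes. In-hospital tests up to discharge will often exist. This stands, but nothing requires a test at stopping or between discharge and Day 14. The rule to repeat abnormal tests operates only once an abnormality has been found.
- **Stopping for a laboratory reason implies a measurement.** Anyone stopped for platelets or ALT/bilirubin already has that result, and Section 8.4.6 requires platelet values for bleeding events. The exposed group is therefore mainly those who stop for improvement or at their own request and go home.
- **The ALT period is counted in days of exposure.** Someone stopping on Days 2–4 does not reach Day 5 of exposure. After a Day 5 stop, a Day 11–17 draw falls 6–12 days after stopping, within the recovery period that Section 4.3 describes, so it may catch a residual rise. This weakens the ALT part for the earliest stoppers, but not the HIT part.

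A reader might also infer more than the documents support:

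- **That completers have unobserved windows.** They have draws on D6, D8 and D14.
- **That aPTT-driven stops on active drug make the missing data arm-related.** An aPTT stop is not a discharge, and those who remain in hospital keep the later draws. Only discharge on improvement could produce an arm difference. The documents give no rate for it, and the Cohort 1 and 2 analyses are descriptive. Bias in the dose decision is not shown.
- **That SAP Figure 3 contradicts Table 1.** Its axis instruction is "Incl Early Tx DC at the end of the x-axis", but its programmer note tells the analyst to adapt visits to each parameter, and the coagulation tests are scheduled at that visit.
- **That a general share discharged before Day 8 sizes the problem.** Any such figure would be an assumption. It would also overcount, because a discharge on Day 7, or on Day 6 after the draw, leaves a sample in both windows.

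**Conclusion.** The concern holds in a limited form. Section 7.2 sends early stoppers to a visit at which Table 1 schedules no platelet count or liver test. With the skip to Day 14, those discharged before the Day 6 draw can go 7–13 days (Day 5 discharge), or up to 16 days (Day 2 discharge with that day's draw missed), without a scheduled result. The gap covers the ALT period and, with a Day 15–17 visit, the whole HIT timing window. SAP Table 14 would show a missed peak as whatever grade was observed, not as Unknown.

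This rests on the Table 1 marks as printed, on 4Ts days counted from Day 1, and on no standard-care test filling the gap. It is a cheap improvement to safety data capture and does not undermine the trial.

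The blank Day 8 aPTT cell is a minor mismatch. Footnote d already asks for at least daily measurement during the infusion, and seven draws over 168 hours (168/24 = 7) could be read as meeting it.

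**What to change.** Reconcile the Early Therapy DC column of Table 1 with Section 7.2 by marking the hematology/chemistry row there. Blood is already scheduled at that visit for PT/INR, aPTT and anti-Xa, so the cost is extra local-laboratory tubes and eCRF entries, with no new visit. The gain is an end-of-exposure ALT and platelet value for every early stopper.

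The remaining gap for Day 2–4 discharges should be acknowledged. Closing it would take a draw between discharge and Day 14, which is a larger burden.

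Separately, make the Day 8 aPTT cell and footnote d agree, so that sites can tell what is required on the last day of infusion. Which reading applies is for the sponsor to decide. This costs one table mark or one clarifying sentence.

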## 2. INTRODUCTION

Dociparstat sodium is being investigated for the treatment of acute lung injury (ALI) associated with severe Coronavirus Disease 2019 (COVID-19) in adults.

### 2.1. Study Rationale

This Phase 2/3 study of dociparstat in participants with ALI associated with severe COVID-19 is being conducted to determine whether dociparstat can be safely and effectively used to mitigate respiratory failure, prevent the need for ventilator support, and reduce excessive coagulation. Dociparstat is a glycosaminoglycan derived from porcine heparin. The pharmacologic activity profile of dociparstat retains the polyanionic and anti-inflammatory activities of unfractionated heparin with substantially reduced anticoagulant activity ([Rao 2010](#)).

Dociparstat may improve outcomes in severe COVID-19 by several mechanisms including:

1. Reducing inflammation
2. Reducing immune cell infiltration
3. Reducing excessive thrombosis

Dociparstat is a well-characterized compound that is also in clinical development for acute myeloid leukemia (AML) and has demonstrated a favorable safety profile in clinical studies for acute exacerbations of chronic obstructive pulmonary disease (COPD), pancreatic cancer, and AML ([Kovacs 2018](#)).

The purpose of this study is to test whether use of dociparstat results in clinical benefit in patients hospitalized with severe COVID-19. This study is being conducted in accordance with the Secretary of the Department of Health and Human Services' (HHS) Declaration under the Public Readiness and Emergency Preparedness (PREP) Act for medical countermeasures against COVID-19 (COVID-19 Declaration) effective 04 February 2020. This study is authorized to proceed under an approved Investigational New Drug application (IND) in accordance with the public health and medical response of the Food and Drug Administration (FDA), an Authority Having Jurisdiction as described under the PREP Act, to prescribe, administer, deliver, distribute, or dispense this Covered Countermeasure as defined by and following the HHS COVID-19 Declaration.

